4.1.3 Exploratory Efficacy Variables

The following parameters will be measured only on UK subjects at 12, 24, 48, 72 and 96 hrs after start of treatment (first dose in the poractant alfa group) or after randomisation (in the control group):

- Change from baseline in Surfactant Function measuring surface tension (mN/m) from TA samples.
- Change from baseline in Mass spec lipid analysis (%) from TA samples.
- Change from baseline in Surfactant Protein D Enzyme Linked Immunosorbent Assay (ng/mL) from TA samples.
- Change from baseline in Surfactant Protein D Enzyme Linked Immunosorbent Assay (ng/mL) from Blood samples.

4.2 Safety Variables

- Adverse events (AEs).
- Laboratory parameters.
- Vital signs (blood pressures and pulse rate).

5 Sample Size

A total of 70 subjects will be randomised in the study with a ratio 3:2 (i.e. 42 subjects randomised to the poractant alfa group and 28 in the control group). Assuming subjects in the control arm being free from ventilation on average 1 week (i.e. 7 days), this sample size achieves 84% power to detect a difference of 4 days (i.e. on average 11 ventilation-free days for subjects treated with poractant alfa), assuming a standard deviation of 5.5 and a two-sided significance level (alpha) of 0.05 using a two-sample t-test.

6 Analysis Set

The definition of the analysis set is summarized below. A final agreement on the subjects to be included in or excluded from the analysis set will be reached during the review of the data

before database lock. Inclusions and exclusions from the analysis set will be fully documented in the Data Review Report.

6.1 Safety Set

All randomised subjects and receive at least one dose of the study treatment (Curosurf treated patients) (analysed as treated). The Safety Set will be used for all safety analyses.

6.2 Intention-To-Treat Set

All randomised subjects who have at least one post baseline efficacy data analysed as randomised. The ITT Set will be used for all efficacy analysis.

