12.2 Populations for analysis

- **Intention-to-Treat population (ITT):** all randomised patients (analysed as randomised).
- **Safety population:** all randomised patients and receive at least one dose of the study treatment (Curosurf treated patients) (analysed as treated).

The primary analysis population for efficacy will be the ITT. The Safety population will be used in the analysis of all safety variables.

Clinical Study Code No.: CLI-050000-04	Version No.: 4.0
EUDRACT No.: 2020-002632-75 – IND No: 153286	Date: 02 MAR 2021

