4.1 Efficacy Variables

4.1.1 Primary Efficacy Variable

The primary efficacy variable is the number of days alive and ventilator-free defined as the number of days the subjects is alive and not receiving mechanical ventilation over the **21 days** following randomisation.

Mechanical ventilation is defined as invasive and non-invasive. Subject is defined as free of mechanical ventilation after 12 hours from the suspension of either invasive or non-invasive ventilation. Subjects who die or are mechanically ventilated longer than this period are assessed as zero ventilator-free days.

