4.1.2.2 Others Secondary Efficacy Variables

- Number of days alive and ventilator-free **at Day 28**
- Mortality **at Day 21 and Day 28**
- Number of days alive and free from invasive ventilation **at Day 21 and Day 28**

- Number of days alive and free from non-invasive ventilation (NIV) at **Day 21 and Day 28**
- Percentage of subjects with improvement in severity status defined as a decrease in the severity score at **Day 28 or Discharge**, whichever comes first. Severity score will be defined as Mild, Moderate, Severe or Death based on PaO₂/FiO₂ ratio and subject status at Day 28 and numerically rated from 1-4 respectively:

Severity	Variable	Criteria
Mild -1	PaO ₂ /FiO ₂ Ratio	200 mmHg < PaO ₂ /FIO ₂ ≤ 300 mmHg
Moderate - 2	PaO ₂ /FiO ₂ Ratio	100 mmHg < PaO ₂ /FIO ₂ ≤ 200 mmHg
Severe - 3	PaO ₂ /FiO ₂	Ratio PaO ₂ /FIO ₂ ≤ 100 mmHg
Death - 4	Patient Status	Yes/No

- Change from baseline in PaO₂/FiO₂ ratio at **6 and 12 hours following administration of each dose** in the treated group and at the similar timepoints in the control group (6, 12, 30, 36, 54 and 60 hours after randomisation)
- Change from baseline in PaO₂/FiO₂ ratio at additional timepoints (i.e. every 24 hours after treatment/randomisation until the subject is discharged from the ICU)
- Percentage of subjects alive and with PaO₂/FiO₂ improvement of >20% at **6 and 12 hours following administration of each dose** in the treated group and at similar timepoints in the control group (6, 12, 30, 36, 54 and 60 hours after randomisation)
- Percentage of subjects alive and with PaO₂/FiO₂ improvement of >20% at the additional timepoints (i.e. every 24 hours after treatment/randomisation till the subject is discharged from the ICU)
- Change from baseline in FiO₂ at **6 and 12 hours following administration of each dose** in the treated group and at similar timepoints in the control group (6, 12, 30, 36, 54 and 60 hours after randomisation)
- Change from baseline in FiO₂ at additional timepoints (i.e. every 24 hours after treatment/randomisation until the subject is discharged from the ICU)
- Length of ICU stay (days) **at Day 28**. Subjects who die or are mechanically ventilated longer than this period are assigned with 28 days
- Percentage of subjects alive and out of ICU **at Day 28**
- Delta SOFA Score and sub-score component measured on **Day 3 and Day 28 or Discharge** whichever comes first

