7.2 Intercurrent Events

Death and Early discontinuation from study drug can be anticipated as intercurrent events:

- Death will be incorporated as a failure outcome for binary endpoints using composite strategy;
- Early discontinuation from study drug will be handled using treatment policy strategy: all data collected after discontinuation from study drug till Day 28 or death will be included;
- Change in respiratory parameters will be analysed using while-alive strategy.

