7.4 Handling of Missing Data

In general, except as described below, missing data will not be imputed.

The number of subjects with missing data will be presented under a “Missing” category. Unless otherwise stated, missing values will not be included in the denominator count when calculating percentages.

When quantitative variables are being summarized, only the non-missing values will be evaluated for calculating summary statistics.

Other critical missing data, if any, will be discussed during the review of the data before database lock. Decisions will be fully documented in the Data Review Report.

Medications: Missing/Incomplete Date

In case of missing or incomplete dates not directly allowing allocation to any category of medications, a worst-case allocation will be done according to the available parts of the start and the stop dates. The medications will be allocated to the first category allowed by the available data, according to the following order:

1. Concomitant medication;
2. Maintained medication;
3. Prior medication.

Procedures: Missing/Incomplete Date

In case of missing or incomplete dates not directly allowing allocation to any category of procedure, a worst-case allocation will be done according to the available parts of the start and the stop dates. The procedure will be allocated to the first category allowed by the available data, according to the following order:

1. Concomitant procedure;
2. Maintained procedure;
3. Prior procedure.

Adverse Events (AEs): Missing/Incomplete Date

In case of missing or incomplete date/time not directly allowing allocation to any of the category of AEs, a worst-case allocation will be done according to the available parts of the start and the stop dates/times. The AE will be allocated to the first category allowed by the available data, according to the following order:

1. Treatment emergent;
2. Pre-treatment.

Adverse Events (AEs): Missing Severity

In case of missing severity, the severity will not be imputed and will be reported as “Missing”. For the table of TEAEs by maximum severity, the maximum severity will be considered as the maximum of the non-missing severities for the relevant subject and preferred term.

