7.13 Listings

All data collected in the eCRF will be presented in the individual listings. All listing will be presented for the ITT set (equal to the randomised set), unless otherwise specified.

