10.4 Laboratory Parameters

Laboratory parameters actual values and change from baseline will be presented using descriptive statistics by timepoint for each treatment group.

An individual subject listing will also be provided for laboratory data.

11 Other Analyses

No other analyses planned. All other data collected in the eCRF will be listed.

12 Changes in the Planned Analyses from Study Protocol

As this study is specifically linked to the COVID-19 pandemic situation, as there was a global improvement in the countries (US, UK, Italy) where the study was done during 2021 (vaccines against COVID-19, better treatment, variant less contagious...), the recruitment was lower than expected and the study was closed before reaching the target sample size of 70 subjects.

As a consequence all statistical analysis planned in the protocol were not done considering the low sample size:

- Statistical Analysis of Days Alive and Free from Ventilation at Day 21
- Subjects alive and free of respiratory failure at Day 28.
- Statistical Analysis of Days Alive and Free from Invasive Ventilation Day 28
- Statistical Analysis of Days Alive and Free from Invasive Ventilation at Day 21 and Day 28
- Statistical Analysis of Days Alive and Free from Non-Invasive Ventilation at Day 21 and Day 28
- Statistical Analysis of Mortality at Day 21 and Day 28
- Statistical Analysis of Proportion of Subjects with Improvement in Severity Status at Day 28/Discharge
- Statistical Analysis of Change from Baseline in pao₂/fio₂ Ratio at Each Timepoint
- Statistical Analysis of Proportion of Subjects with pao₂/fio₂ Ratio Improvement >20% Compared to Baseline at Each Timepoint
- Statistical Analysis of Change from Baseline in fio₂ at Each Timepoint
- Statistical Analysis of Length of ICU Stay (Days) at Day 28
- Statistical Analysis of Proportion of Subjects Alive and Out of ICU at Day 28
- Statistical Analysis of Delta SOFA Score at Day 3 and Day 28/ Discharge
- Statistical Analysis of Delta SOFA Sub Score at Day 3 and Day 28/Discharge
- Statistical Analysis of Proportion of Subjects Alive and Organ Failure Free at Day 28/Discharge

ITT definition was changed from “all randomised patients (analysed as randomised)” to “all randomised subjects who have at least one post baseline efficacy data analysed as randomised”.

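### SAP 6.2 adds an undefined data condition to the protocol's ITT set that may act unequally by arm, and SAP 6.1 read literally leaves no controls in the Safety Set; effect unknown and possibly nil

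*SAP*

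**What the plan says.** **ITT set.** Protocol 12.2 defines ITT as "all randomised patients (analysed as randomised", with no data condition. SAP 6.2 has "All randomised subjects who have at least one post baseline efficacy data analysed as randomised" and uses this set for all efficacy analyses. SAP Section 12 states that the "ITT definition was changed from" the protocol wording to the new one. Its low-recruitment explanation introduces the list of dropped statistical analyses; no separate reason is attached to the ITT change. SAP 7.13 says "All listing will be presented for the ITT set (equal to the randomised set), unless otherwise specified".

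**What counts as post-baseline.** SAP 7.9.1 takes baseline as the last value before randomisation in the control group, but before the first dose in the poractant alfa group. Efficacy data are not defined.

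**Deaths.** Three places treat death as an efficacy outcome. SAP 4.1.2.2 lists "Mortality at Day 21 and Day 28" as a secondary efficacy variable. SAP 4.1.1 says "Subjects who die or are mechanically ventilated longer than this period are assessed as zero ventilator-free days". SAP 7.2 says "Death will be incorporated as a failure outcome for binary endpoints using composite strategy".

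**Safety Set.** SAP 6.1 requires at least one dose of study treatment and adds in brackets that these are Curosurf-treated patients. Protocol 12.2 has the same wording. Yet SAP 8.4 and 8.5 give control-group rules for Safety Set summaries, SAP 10.2 defines treatment-emergent events for controls from randomisation, and Safety Set tables such as 14.3.1 call for both treatment columns.

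**The concern.** An ITT set conditioned on post-randomisation data is not the set that randomisation protects. Here the condition also has a different starting point in each arm. The trial is open-label: allocation is known once the envelope is opened (protocol 6.6), and the first dose may follow up to 2 hours later (protocol 7.1.2). A poractant alfa subject who is withdrawn, dies or is otherwise never dosed has no first dose from which post-baseline can be counted. A control with the same course does have a baseline time point. Taken literally, exclusions could fall on one arm only.

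The stakes are limited but real. The primary result is now a descriptive mean by arm (SAP 7.5, 9.1), so who is in the denominator matters directly, and a table labelled ITT would be read as covering everyone randomised. A dosed subject outside the ITT set would also appear in Safety Set adverse-event tables but not in their source listings, which use the ITT set (SAP 16.1 and 16.2).

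For safety, a programmer who applies 6.1 literally would have no control data to put in the control columns.

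**Working it through.** **1. The plan's own figure.** Inputs from SAP Section 5: 42 and 28 subjects, means 11 and 7 days, SD 5.5, two-sided alpha 0.05. The standard error is 5.5 × √(1/42 + 1/28) = 1.342, and 4/1.342 = 2.981. The normal approximation gives Φ(2.981 − 1.960) = 84.6%; the noncentral t gives 83.6%. The stated 84% is reproduced. It assumes all 70 randomised subjects are analysed.

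**2. The definitions side by side.** Protocol 12.2: randomised. SAP 6.2: randomised and with at least one post-baseline efficacy datum. SAP 7.13: equal to randomised. The last two agree only if no randomised subject fails the condition. If nobody fails, the condition does nothing; if somebody fails, the set is not the protocol's ITT set.

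**3. Effect if a zero score is dropped.** If one subject with 0 ventilator-free days leaves an arm of size n and mean m, the mean rises by m·n/(n−1) − m = m/(n−1).
- Poractant alfa, n = 42, m = 11: 11/41 = 0.268 days.
- Control, n = 28, m = 7: 7/27 = 0.259 days.
- Difference between arms, planned at 4.00: one dropped in poractant alfa only, 11.268 − 7 = 4.27; in control only, 11 − 7.259 = 3.74; one in each, 11.268 − 7.259 = 4.01.

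SAP Section 12 says the study closed before 70 and gives no arm sizes. For assumed poractant alfa arms of 24 and 12 with mean 11, the rise is 11/23 = 0.48 and 11/11 = 1.00 days.

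**4. Mortality, if the dropped subject is a death.** The fall is d/n − (d−1)/(n−1) for d deaths. Protocol 1.1 expects 30–70% ICU mortality, assumed here for each arm.
- n = 28: d = 8 gives 28.6% to 25.9% (2.6 points); d = 20 gives 71.4% to 70.4% (1.1 points).
- n = 42: d = 13 gives 31.0% to 29.3% (1.7 points); d = 29 gives 69.0% to 68.3% (0.8 points).

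**5. Effect if only subjects with no data are dropped.** SAP 7.4 says "only the non-missing values will be evaluated for calculating summary statistics", which suggests no change. Two endpoint rules could still give such a subject a value. SAP 9.3.3 sets non-invasive-ventilation-free days to 21 (or 28) if that ventilation was never started. SAP 9.3.6 puts every change not above 20% in the other category through an *else*. Under 9.3.3 at Day 21, including one such subject shifts the arm mean by (21 − m)/n, where m is the mean of the others; this is at most 21/42 = 0.50 or 21/28 = 0.75 days. Under 9.3.6 it lowers the responder percentage by at most 1/42 = 2.4 or 1/28 = 3.6 points.

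**6. Safety Set.** Literal 6.1 at planned size: up to 42 poractant alfa subjects and 0 of 28 controls. With the dose condition applied to the poractant alfa arm only: up to 70.

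**The case against.** The case for leaving this alone is substantial. The ITT change is declared, with old and new wording together. Set membership is agreed before database lock and documented in the Data Review Report (SAP Section 6). Listing 16.2.3.2 gives the reason for any exclusion, and set sizes by arm are tabulated (SAP 8.1.3, Table 14.1.1.4). Eligible patients are already intubated, ventilatory support is scheduled throughout, and deaths carry efficacy values, so nearly every randomised subject should have a qualifying datum. Ventilator-free days are counted from randomisation, so a sensible programmer would include a never-dosed subject. SAP 7.13 may simply record that nobody failed the condition. No hypothesis test depends on it. On safety, the bracketed phrase in 6.1 can be read as saying to whom the dose condition applies, and the control-arm rules make the intent clear.

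Most of that stands, and it limits the severity. It does not remove the mismatch: whether a never-dosed subject or a death before the first scheduled reading qualifies is left to judgement in an open-label trial. Disclosure of exclusions tells the reader that the set was narrowed; it does not restore it.

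A reader might infer that early deaths were dropped to improve the result, or that controls will be missing from the safety tables. The documents support neither: no exclusion is shown, deaths most likely qualify, and controls are plainly intended. Nor do they support the opposite inference, that no summary can move, because of SAP 9.3.3 and 9.3.6.

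**Conclusion.** The textual defects are certain; their consequence is not. SAP 6.2 is narrower than the protocol's ITT set, fits 7.13 only if it excludes nobody, rests on an undefined term, and can literally treat never-dosed poractant alfa subjects differently from controls. Because SAP Section 12 declares it as a change of population, it is more than loose wording. SAP 6.1 is a wording defect shared with the protocol.

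The effect on results is unknown and possibly zero. The shifts of about 0.27 and 0.26 days per dropped zero score assume the planning means, the planned arm sizes and the exclusion of a subject scored zero. They would be larger in smaller arms at the same means. Severity: minor to should-fix.

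**What to change.** - **SAP 6.2:** *all randomised subjects, analysed as randomised*. Score deaths as each endpoint specifies. Show subjects with no outcome data as missing, by arm, and say that this also governs 9.3.3 and 9.3.6, so that neither rule assigns them a value.
- **SAP Section 12:** delete the sentence on the ITT change; 7.13 then holds as written. Report by arm how many subjects the condition would have removed. If the answer is none, the matter closes.
- **SAP 6.1:** *all subjects randomised to control, plus subjects randomised to poractant alfa who received at least one dose, analysed by treatment received*. Because the protocol has the same unclear wording, add this to Section 12 as a clarification of the protocol's Safety population.
- **If outputs have already been run:** record both definitions as deviations in the CSR, as SAP Section 1 provides.

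The cost is a short SAP revision or CSR note, two population flags and a check of two derivations. No new data and no protocol amendment are needed.

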6.3 Other Populations Defined for Tables and Listings

For the purposes of tables and listings the following population is defined:

- Enrolled Set: all subjects who have a signed informed consent for the study.

Note: the informed consent can be signed by subject himself when feasible or, in case of unconscious subject, by a third party (legal representative or by the physician only) according to the local regulations and the pre-defined rules suitable for a trial conducted at Intensive Care Units. In case the subject is consented to the study by a third party and they regain capacity, the participant was informed and their consent was requested to continue the participation in the trial.

7 General Considerations for Statistical Analysis

7.1 Statistical Significance

All tests of hypotheses will be two-sided and conducted at the 0.05 significance level, and all confidence intervals will be two-sided at the 95% confidence level, if applicable.

7.2 Intercurrent Events

Death and Early discontinuation from study drug can be anticipated as intercurrent events:

- Death will be incorporated as a failure outcome for binary endpoints using composite strategy;
- Early discontinuation from study drug will be handled using treatment policy strategy: all data collected after discontinuation from study drug till Day 28 or death will be included;
- Change in respiratory parameters will be analysed using while-alive strategy.

7.3 Multiplicity

No multiplicity adjustment will be performed.

7.4 Handling of Missing Data

In general, except as described below, missing data will not be imputed.

The number of subjects with missing data will be presented under a “Missing” category. Unless otherwise stated, missing values will not be included in the denominator count when calculating percentages.

When quantitative variables are being summarized, only the non-missing values will be evaluated for calculating summary statistics.

Other critical missing data, if any, will be discussed during the review of the data before database lock. Decisions will be fully documented in the Data Review Report.

Medications: Missing/Incomplete Date

In case of missing or incomplete dates not directly allowing allocation to any category of medications, a worst-case allocation will be done according to the available parts of the start and the stop dates. The medications will be allocated to the first category allowed by the available data, according to the following order:

1. Concomitant medication;
2. Maintained medication;
3. Prior medication.

Procedures: Missing/Incomplete Date

In case of missing or incomplete dates not directly allowing allocation to any category of procedure, a worst-case allocation will be done according to the available parts of the start and the stop dates. The procedure will be allocated to the first category allowed by the available data, according to the following order:

1. Concomitant procedure;
2. Maintained procedure;
3. Prior procedure.

Adverse Events (AEs): Missing/Incomplete Date

In case of missing or incomplete date/time not directly allowing allocation to any of the category of AEs, a worst-case allocation will be done according to the available parts of the start and the stop dates/times. The AE will be allocated to the first category allowed by the available data, according to the following order:

1. Treatment emergent;
2. Pre-treatment.

Adverse Events (AEs): Missing Severity

In case of missing severity, the severity will not be imputed and will be reported as “Missing”. For the table of TEAEs by maximum severity, the maximum severity will be considered as the maximum of the non-missing severities for the relevant subject and preferred term.

7.5 Covariates

Not applicable. All data will be summarized by means of descriptive statistics.

7.6 Interim Analyses

No interim analysis will be performed.

7.7 Examinations of Subgroups

Exploratory parameters from TA aspirates and blood samples will only be analysed for UK subjects.

7.8 Descriptive Statistics

General descriptive statistics for quantitative variables will include the n (the number of non-missing values), the mean, the standard deviation (SD), the median, the minimum (min) and the maximum values (max).

For categorical variables, the number (n) and percentage (%) of subjects with a specific level of the variable will be presented. The number of missing values will be displayed as a “Missing” category, where appropriate. Unless otherwise specified, the denominator for each percentage will be the number of non-missing observations within the analysis set and treatment group.

